## 9. STATISTICAL METHODOLOGY

### 9.1 General

Data listings will be provided for all data that is databased. Summary statistics and statistical analysis will only be presented for data where detailed in this SAP. For continuous data, summary statistics will include the arithmetic mean, arithmetic standard deviation (SD), median, min, max and N; for log-normal data (e.g. the PK parameters: area under the concentration time curve [AUC] and maximum observed drug concentration [ $C_{max}$ ]) the geometric mean and geometric coefficient of variation (CV%) will also be presented. For categorical data, frequency

count and percentages will be presented. Data listings will be provided for all subjects up to the point of withdrawal, with any subjects excluded from the relevant population highlighted. Summary statistics and statistical analyses will generally only be performed for subjects included in the relevant analysis population. For the calculation of summary statistics and statistical analysis, unrounded data will be used.

Mean change from baseline is the mean of all individual subjects' change from baseline values. Each individual change from baseline will be calculated by subtracting the individual subject's baseline value from the value at the time point. The individual subject's change from baseline values will be used to calculate the mean change from baseline using a SAS procedure such as Proc Univariate.

No adjustments for multiple comparisons will be made.

Data analysis will be performed using SAS® Version 9.4 or greater.

## **9.2 Demographics and Subject Disposition**

Subject disposition will be listed. The demographic variables age, sex, race, ethnicity, country of enrolment, site ID, body weight, height and body mass index (BMI) will be summarized and listed. All other demographic variables, including associated person demographics, will be listed only.

## **9.3 Pharmacokinetic Assessment**

### **9.3.1 Pharmacokinetic Analysis**

The PK parameter estimates will be determined for LY3074828 using non-compartmental procedures with a validated software program CCI

Serum concentrations of LY3074828 will be used to determine the following PK parameters, when possible:

| Parameter                  | Units           | Definition  |
|----------------------------|-----------------|---|
| AUC(0-t last )  | day* $\mu$ g/mL | area under the concentration versus time curve from time zero to time t, where t is the last time point with a measurable concentration |
| AUC(0-∞)                   | day* $\mu$ g/mL | area under the concentration versus time curve from time zero to infinity   |
| %AUC(t last -∞) | %               | percentage of AUC(0-∞) extrapolated   |
| C max           | $\mu$ g/mL      | maximum observed drug concentration   |
| t max           | day             | time of maximum observed drug concentration   |
| t 1/2           | day             | half-life associated with the terminal rate constant ( $\lambda_z$ ) in non-compartmental analysis                                      |
| CL                         | L/day           | total body clearance of drug calculated after extra-vascular administration   |
| CL/F                       | L/day           | apparent total body clearance of drug calculated after IV administration  |
| V z             | L               | volume of distribution during the terminal phase after IV administration  |
| V z /F          | L               | apparent volume of distribution during the terminal phase after extra-vascular administration   |
| V ss            | L               | volume of distribution at steady state after IV administration  |
| V ss /F         | L               | apparent volume of distribution at steady state after extra-vascular administration   |
| F                          | %               | absolute bioavailability  |
| F (pooled)                 | %               | absolute bioavailability of pooled 200 mg and 400 mg SC treatments  |

Additional PK parameters may be calculated, as appropriate. The software and version used for the final analyses will be specified in the clinical study report. Any exceptions or special handling of data will be clearly documented within the final study report.

Estimates of absolute bioavailability will be made as follows:

$$F = \frac{\text{Geo Mean AUC}(0 - \infty)/D \text{ (200 mg or 400 mg SC)}}{\text{Geo Mean AUC}(0 - \infty)/D \text{ (pooled 300 mg, 600 mg & 1200 mg IV)}} \times 100$$

and

$$F \text{ (pooled)} = \frac{\text{Geo Mean AUC}(0 - \infty)/D \text{ (pooled 200 mg & 400 mg SC)}}{\text{Geo Mean AUC}(0 - \infty)/D \text{ (pooled 300 mg, 600 mg & 1200 mg IV)}} \times 100$$

where AUC(0-∞)/D = AUC(0-∞) divided by dose.

CCI

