10.3.2. Pharmacokinetic Analyses

10.3.2.1. Pharmacokinetic Parameter Estimation

Pharmacokinetic parameter estimates for LY3074828 will be calculated by standard noncompartmental methods of analysis.

The primary parameters for analysis will be AUC from time zero to infinity (AUC[0-∞]), AUC from time zero to time t, where t is the last sample with a measurable concentration (AUC[0-t_{last}]), and maximum observed drug concentration (C_{max}) for LY3074828. The secondary parameter for analysis will be the time to maximum observed drug concentration (t_{max}) of LY3074828. Other PK parameters, such as bioavailability following SC administration, t_{1/2}, clearance, and volume of distribution (apparent clearance and apparent volume of distribution for SC administration), may be reported.

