Appendix 1. Abbreviations and Definitions

Term	Definition
ADA	anti-drug antibody
AE	adverse event: Any untoward medical occurrence in a patient or clinical investigation subject administered a pharmaceutical product that does not necessarily have a causal relationship with this treatment. An AE can therefore be any unfavorable and unintended sign (including an abnormal laboratory finding), symptom, or disease temporally associated with the use of a medicinal (investigational) product, whether or not related to the medicinal (investigational) product.
ALP	alkaline phosphatase
ALT	alanine aminotransferase
AUC	area under the concentration versus time curve
AUC(0-∞)	area under the concentration versus time curve from time zero to infinity
AUC(0-t_{last})	area under the concentration versus time curve from time zero to time t, where t is the last sample with a measurable concentration
BMI	body mass index
CD	Crohn's disease
CL/F	apparent total body clearance of drug calculated after extra-vascular administration
C_{max}	maximum observed drug concentration
complaint	A complaint is any written, electronic, or oral communication that alleges deficiencies related to the identity, quality, purity, durability, reliability, safety or effectiveness, or performance of a drug or drug delivery system.
compliance	Adherence to all the study-related requirements, good clinical practice (GCP) requirements, and the applicable regulatory requirements.
confirmation	A process used to confirm that laboratory test results meet the quality requirements defined by the laboratory generating the data and that Lilly is confident that results are accurate. Confirmation will either occur immediately after initial testing or will require that samples be held to be retested at some defined time point, depending on the steps required to obtain confirmed results.
CP	clinical pharmacologist
CRP	clinical research physician: Individual responsible for the medical conduct of the study. Responsibilities of the CRP may be performed by a physician, clinical research scientist, global safety physician or other medical officer.
CRU	clinical research unit
ECG	electrocardiogram
eCRF	electronic case report form

enroll	The act of assigning a subject to a treatment. Subjects who are enrolled in the study are those who have been assigned to a treatment.
enter	Subjects entered into a study are those who sign the informed consent form directly or through their legally acceptable representatives.

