## 2. ABBREVIATIONS

Abbreviations pertain to the Statistical Analysis Plan (SAP) only (not the tables, figures and listings [TFLs]).

|                            |   |
|----------------------------|---|
| AE                         | Adverse event   |
| ADA                        | Anti-drug antibody  |
| ALP                        | Alkaline phosphatase  |
| ALT                        | Alanine aminotransferase  |
| AUC                        | Area under the concentration versus time curve  |
| AUC(0-t last )  | Area under the concentration versus time curve from time zero to time t, where t is the last time point with a measurable concentration |
| AUC(0-∞)                   | Area under the concentration versus time curve from time zero to infinity   |
| %AUC(t last -∞) | Percentage of AUC(0-∞) extrapolated   |
| BMI                        | Body mass index   |
| BQL                        | Below the lower limit of quantification   |
| C last          | Last quantifiable drug concentration  |
| C max           | Maximum observed drug concentration   |
| CI                         | Confidence interval   |
| CL/F                       | Apparent total body clearance of drug calculated after extra-vascular administration  |
| CRF                        | Case Report Form  |
| CRU                        | Clinical Research Unit  |
| CSR                        | Clinical Study Report   |
| CV                         | Coefficient of variation  |
| EC                         | Early Clinical  |
| ECG                        | Electrocardiogram   |
| e.g.                       | For example (Latin: exempli gratia )   |
| F                          | Fraction of extravascular dose reaching the general circulation compared to an IV administration  |
| ICH                        | International Conference on Harmonisation   |
| IV                         | Intravenous   |
| LLOQ                       | Lower limit of quantification   |
| MedDRA                     | Medical Dictionary for Regulatory Activities  |

---

|            |  |
|------------|--|
| MRE        | Magnetic resonance elastography  |
| PK         | Pharmacokinetic  |
| SAP        | Statistical Analysis Plan  |
| SC         | Subcutaneous   |
| SD         | Standard deviation   |
| SOP        | Standard Operating Procedure   |

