| $t_{1/2}$  | Half-life associated with the terminal rate constant ( $\lambda_z$ ) in non-compartmental analysis |
| TBL        | Total bilirubin  |
| CCI | [REDACTED]   |
| TEAE       | Treatment-emergent adverse event   |
| TFLs       | Tables, Figures, and Listings  |
| $t_{max}$  | Time of maximum observed drug concentration  |
| ULN        | Upper limit of normal  |
| $V_{ss}$   | Volume of distribution at steady state after intravenous administration                            |
| $V_{ss/F}$ | Apparent volume of distribution at steady state after extra-vascular administration                |
| $V_z$      | Volume of distribution during the terminal phase after IV administration                           |
| $V_z/F$    | Apparent volume of distribution during the terminal phase after extra-vascular administration      |
| WHO        | World Health Organization  |

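### Do the exchanged routes in the SAP's CL and CL/F definitions affect the pharmacokinetic analysis?

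*SAP*

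**What the plan says.** SAP 9.3.1 lists the noncompartmental parameters to be derived when possible. Its CL row reads "total body clearance of drug calculated after extra-vascular administration" and its CL/F row reads "apparent total body clearance of drug calculated after IV administration".

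Other places pair symbol and route the other way round:

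- The SAP abbreviation list (section 2) gives CL/F as "Apparent total body clearance of drug calculated after extra-vascular administration".
- Protocol Appendix 1 gives the same meaning: "apparent total body clearance of drug calculated after extra-vascular administration".
- Protocol 10.3.2.1 names clearance and volume among the optional parameters and adds in brackets "apparent clearance and apparent volume of distribution for SC administration".
- In the SAP 9.3.1 table itself, Vz is "volume of distribution during the terminal phase after IV administration" and Vss/F is "apparent volume of distribution at steady state after extra-vascular administration".

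Neither abbreviation list has an entry for CL alone. The formulas for F and F (pooled), which follow the table in SAP 9.3.1, use geometric mean AUC(0-∞) divided by dose.

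**The concern.** A clearance written without F is the true clearance, which a study of this kind can obtain only from IV data. With F it is the apparent clearance from SC data. The table says the opposite for both symbols.

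This trial doses by both routes, so both symbols will be used. SAP 3 says that the SAP supersedes the protocol's statistical considerations and that, with its table shells, it will be the template for the study report. If the shells copy the table literally, SC apparent clearance would appear as CL and IV clearance as CL/F. A reader who took the SC figure as true clearance would have it too high by a factor of 1/F. Because CL is in neither abbreviation list, the faulty row is the only place where that symbol is spelled out.

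**Working it through.** **1. Is it a slip or a change of plan?** The definitions side by side:

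| Symbol | SAP 9.3.1 table | SAP 2 list | Protocol Appendix 1 | Protocol 10.3.2.1 |
|---|---|---|---|---|
| CL | extravascular | no entry | no entry | clearance, without the SC qualifier |
| CL/F | IV | extravascular | extravascular | apparent clearance, SC |
| Vz | IV | IV | no entry | volume, without the SC qualifier |
| Vz/F | extravascular | extravascular | extravascular | apparent volume, SC |
| Vss | IV | IV | no entry | – |
| Vss/F | extravascular | extravascular | no entry | – |

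Only the two clearance cells in the SAP 9.3.1 column break the pattern. The SAP list also defines F as the fraction of an extravascular dose that reaches the circulation, so dividing by F has meaning only for SC data. SAP 3 undertakes to identify substantial departures from the protocol, and SAP 11 reports none. The SAP was written against the original protocol and amendment (a), and the protocol supplied is amendment (c). The changes listed for (c) concern the number of sites, so the inference is unaffected. This is a slip.

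**2. Does any computed value depend on it?** For each subject the noncompartmental calculation is the same on either route:

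- IV subject: dose / AUC(0-∞) = CL
- SC subject: dose / AUC(0-∞) = CL/F

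The route definition decides only the name printed on the result. Then:

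- F and F (pooled) are ratios of geometric mean AUC(0-∞)/dose, SC over pooled IV. Neither CL nor CL/F enters.
- The listed PK endpoints are Cmax, AUC(0-tlast), AUC(0-∞) and tmax. None uses clearance.
- The primary endpoints are treatment-emergent adverse events and the pain VAS score.
- The sample size is 5 cohorts × 12 = 60, with no power calculation behind it.

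Swapping the two definitions therefore changes no number in the plan.

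**3. How large could a misreading be?** The ratio of the two quantities is (CL/F) / CL = 1/F.

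- At the 40% reported for Study AMAA in Protocol 3.2: 1 / 0.40 = 2.5
- At an assumed F of 60%: 1 / 0.60 = 1.67
- At an assumed F of 30%: 1 / 0.30 = 3.33

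The 40% is itself soft: by Protocol 3.2, that study gave SC doses to 5 healthy subjects and IV doses to subjects with psoriasis. The 30% to 60% range is an assumption.

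**4. Would the misreading survive to the report?** SAP 6 names every treatment in the outputs with its route, and SAP 9.3.2 summarises parameters by treatment. A literal copy would print CL against the 200 mg SC and 400 mg SC columns and CL/F against the three IV columns, which a pharmacokineticist would recognise as wrong.

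**The case for a change.** The best argument for acting is that the correction is free and the SAP outranks the protocol on statistical matters, so correct wording in the protocol does not cure the table by itself. The shells are not among the documents, so nobody can show from them that the error stops at the SAP.

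Part of this stands. The table is wrong, and anyone finalising the shells should use the conventional labels. But the cure does not depend on the protocol: the SAP's own abbreviation list has CL/F right, its definition of F fixes the route, and its volume rows show the intended pattern. Adding CL to the abbreviation list would not reach the outputs, because that list is stated to cover the SAP only. Clearance is also optional in the protocol. What remains is an erratum.

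A related question is whether F and F (pooled) should carry a confidence interval. They are single ratios between separate groups, so the standard deviations and ranges in SAP 9.1 do not describe their precision. Against that, text after the formulas is blacked out, so no omission is shown. The visible plan is also descriptive by design: SAP 9.1 lists no interval and SAP 9.3.2 plans no formal analysis. An interval would be a preference here, and its width would rest on a between-subject variability that the documents do not give.

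**Conclusion.** The routes in the CL and CL/F rows of SAP 9.3.1 are exchanged. The mistake is clerical: no endpoint, parameter value, bioavailability estimate or sample size moves, and the correct reading can be recovered from the SAP alone. The factor of 2.5 (1.67 to 3.33 over the assumed range of F) measures a hypothetical misreading of a label, against tables in which the route is printed beside each value. No output error is demonstrated.

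The conclusion assumes that clearance is calculated in the usual way from dose and AUC(0-∞), and that those preparing the report label it by route, as both documents do elsewhere. Correcting the wording is ordinary editorial housekeeping. It brings no gain in any result, and the analysis plan can stand as it is.

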## General PK Parameter Rules

- Actual sampling times will be used in the final analyses of individual PK parameters, except for non-bolus pre-dose sampling times which will be set to zero.
- $C_{max}$  and  $t_{max}$  will be reported from observed values. If  $C_{max}$  occurs at more than one time point,  $t_{max}$  will be assigned to the first occurrence of  $C_{max}$ .
- AUC parameters will be calculated using a combination of the linear and logarithmic trapezoidal methods (linear-log trapezoidal rule). The linear trapezoidal method will be applied up to  $t_{max}$  and then the logarithmic trapezoidal method will be used after  $t_{max}$ . The minimum requirement for the calculation of AUC will be the inclusion of at least three consecutive concentrations above the lower limit of quantification (LLOQ), with at least one of these concentrations following  $C_{max}$ .
- AUC(0-∞) values where the percentage of the total area extrapolated is more than 20% will be flagged. Any AUC(0-∞) value excluded from summary statistics will be noted in the footnote of the summary table.
- Half-life ( $t_{1/2}$ ) will be calculated, when appropriate, based on the apparent terminal log-linear portion of the concentration-time curve. The start of the terminal elimination phase for each subject will be defined by visual inspection and generally will be the first point at which there is no systematic deviation from the log-linear decline in serum concentrations. Half-life will only be calculated when a reliable estimate for this parameter can be obtained comprising of at least 3 data points. If  $t_{1/2}$  is estimated over a time window of less than 2 half-lives, the values will be flagged in the data listings. Any  $t_{1/2}$  value excluded from summary statistics will be documented in the footnote of the summary table.
- A uniform weighting scheme will be used in the regression analysis of the terminal log-linear portion of the concentration-time curve.
- The parameters based on the observed last quantifiable drug concentration ( $C_{last}$ ) will be reported.

## Individual PK Parameter Rules

- Only quantifiable concentrations will be used to calculate PK parameters with the exception of special handling of certain concentrations reported below the lower limit of quantification (BQL). Serum concentrations reported as BQL will be set to a value of zero when all of the following conditions are met:
  - The compound is non-endogenous.
  - The samples are from the initial dose period for a subject or from a subsequent dose period following a suitable wash-out period.

- The time points occur before the first quantifiable concentration.
- All other BQL concentrations that do not meet the above criteria will be set to missing.
- Also, where two or more consecutive concentrations are BQL towards the end of a profile, the profile will be deemed to have terminated and therefore any further quantifiable concentrations will be set to missing for the calculation of the PK parameters unless it is considered to be a true characteristic of the profile of the drug.

### **Individual Concentration vs. Time Profiles**

- Individual concentrations will be plotted utilizing actual sampling times.
- The terminal point selections will be indicated on a semi-logarithmic plot.

### **Average Concentration vs. Time Profiles**

- The average concentration profiles will be graphed using scheduled (nominal) sampling times.
- The average concentration profiles will be graphed using arithmetic average concentrations.
- The pre-dose average concentration for single-dose data from non-endogenous compounds will be set to zero. Otherwise, only quantifiable concentrations will be used to calculate average concentrations.
- Concentrations at a sampling time exceeding the sampling time window specified in the protocol, or  $\pm 10\%$ , will be excluded from the average concentration profiles.
- Concentrations excluded from the mean calculation will be documented in the final study report.
- A concentration average will be plotted for a given sampling time only if 2/3 of the individual data at the time point have quantifiable measurements that are within the sampling time window specified in the protocol or  $\pm 10\%$ . An average concentration estimated with less than 2/3 but more than 3 data points may be displayed on the mean concentration plot if determined to be appropriate and will be documented within the final study report.

### **Treatment of Outliers during Pharmacokinetic Analysis**

Application of this procedure to all PK analyses is not a requirement. Rather, this procedure provides justification for exclusion of data when scientifically appropriate. This procedure describes the methodology for identifying an individual value as an outlier for potential

exclusion, but does not require that the value be excluded from analysis. The following methodology will not be used to exclude complete profiles from analysis.

#### Data within an Individual Profile

A value within an individual profile may be excluded from analysis if any of the following criteria are met:

- For PK profiles during single dosing of non-endogenous compounds, the concentration in a pre-dose sample is quantifiable.
- For any questionable datum that does not satisfy the above criteria, the profile will be evaluated and results reported with and without the suspected datum.

#### Data between Individual Profiles

1. If  $n < 6$ , then the dataset is too small to conduct a reliable range test. Data will be analyzed with and without the atypical value, and both sets of results will be reported.
2. If  $n \geq 6$ , then an objective outlier test will be used to compare the atypical value to other values included in that calculation:
  - a. Transform all values in the calculation to the logarithmic domain.
  - b. Find the most extreme value from the arithmetic mean of the log transformed values and exclude that value from the dataset.
  - c. Calculate the lower and upper bounds of the range defined by the arithmetic mean  $\pm 3 \times \text{SD}$  of the remaining log-transformed values.
  - d. If the extreme value is within the range of arithmetic mean  $\pm 3 \times \text{SD}$ , then it is not an outlier and will be retained in the dataset.
  - e. If the extreme value is outside the range of arithmetic mean  $\pm 3 \times \text{SD}$ , then it is an outlier and will be excluded from analysis.

If the remaining dataset contains another atypical datum suspected to be an outlier and  $n \geq 6$  following the exclusion, then repeat step 2 above. This evaluation may be repeated as many times as necessary, excluding only one suspected outlier in each iteration, until all data remaining in the dataset fall within the range of arithmetic mean  $\pm 3 \times \text{SD}$  of the log-transformed values.

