#### Reporting of Excluded Values

Individual values excluded as outliers will be documented in the final report. Approval of the final report will connote approval of the exclusion.

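### The SAP's PK outlier rule is mandatory in step 2e but optional in its preamble, and at the planned cohort size it requires no summary that keeps the removed value

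*SAP*

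**What the plan says.** SAP 9.3.1 has a subsection on the treatment of outliers during PK analysis. Its preamble makes use optional ("Application of this procedure to all PK analyses is not a requirement") and says the method identifies values for potential "exclusion, but does not require that the value be excluded from analysis".

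The part on data between individual profiles then splits by sample size.

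- **Fewer than six values:** no range test is run. "Data will be analyzed with and without the atypical value, and both sets of results will be reported".
- **Six or more values:** "an objective outlier test will be used to compare the atypical value to other values included in that calculation". The values are logged, the most extreme one is set aside, and the mean ± 3 SD of the rest is computed. If the extreme lies outside that range, "then it is an outlier and will be excluded from analysis". While six or more values remain, "This evaluation may be repeated as many times as necessary", one value at a time.

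For questionable data inside one subject's profile, the SAP again asks for both versions: "the profile will be evaluated and results reported with and without the suspected datum".

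On disclosure, the SAP says "Individual values excluded as outliers will be documented in the final report". SAP 9.1 lists all databased data. The General PK Parameter Rules require a summary-table footnote for excluded AUC(0-∞) and half-life values. They state none for Cmax or AUC(0-tlast).

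**The concern.** There are three linked problems.

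1. **Status of a flagged value.** Read alone, step 2e makes deletion automatic. Read under the preamble, deletion is discretionary, but nothing says when a flagged value is kept or dropped. Two analysts could follow the same SAP and produce different tables.
2. **Missing summary.** The SAP shows both results for small samples and for within-profile data, but not at the sample size the trial plans to have.
3. **Strictness of the limit.** A 3 SD rule sounds as if it would touch only gross errors. Here the SD excludes the suspect value, so with 10 or fewer subjects a valid value can cross the limit.

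No formal PK analysis is planned, so the geometric mean and geometric CV by treatment are the PK result. Deleting a flagged value always lowers that cohort's reported between-subject CV. It also moves the geometric mean, up or down, and the bioavailability estimate F if the value is left out there too.

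**Working it through.** The plan gives no figure for how this rule behaves, so there is none to reproduce. The inputs are 10 active subjects per cohort with no replacement of withdrawals (Protocol 5.1 and 5.2; SAP 5 and 7), and the log-scale, leave-one-out, 3 SD rule (SAP 9.3.1). CVs of 20, 30 and 40% are assumptions for illustration, because the documents give none.

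**Minimum loss of SD.** Let s be the SD of the n−1 remaining log values and d the distance of the removed value from their mean. The whole-cohort variance is

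[(n−2)s² + ((n−1)/n)d²] / (n−1).

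Deletion requires d > 3s. At d = 3s, whole-cohort SD / s = √{[(n−2) + 9(n−1)/n] / (n−1)}. For n=10 this is √[(8 + 8.1)/9] = 1.3375, so the SD falls by 1 − 1/1.3375 = 25.2%. A more extreme value gives a larger fall. No distribution is assumed.

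**The limit in whole-cohort SDs.** The extreme lies (n−1)/n × 3s from the whole-cohort mean. For n=10 that is 2.7s / 1.3375s = 2.02.

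**Upper bound on loss of valid values.** Suppose every cohort's extreme were tested and every flag deleted. For clean log-normal data the chance of at least one deletion per parameter is n × 2 × P(t with n−2 df > 3/√(1 + 1/(n−1))). At n=10 the cut-off is 3/√(10/9) = 2.846.

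| n | Minimum SD cut | Limit in whole-cohort SDs | Upper-bound rate | Simulated rate (400,000 cohorts) |
|---|---|---|---|---|
| 10 | 25.2% | 2.02 | 21.6% | 21.6% |
| 8 | 29.0% | 1.86 | 24.7% | 24.7% |
| 6 | 34.1% | 1.65 | 31.2% | 31.2% |

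With the permitted repeats, 4.9% of clean n=10 cohorts lose two or more values.

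**Effect on the reported CV at n=10.** With σ = √ln(1 + CV²), dividing σ by 1.3375 and converting back turns a cohort CV of 20/30/40% into at most 14.9/22.2/29.4%.

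**Typical effect in affected clean n=10 cohorts (simulation).**

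| Assumed true CV | Mean CV with the value | After one deletion | With repeats | Median shift in geometric mean, one deletion |
|---|---|---|---|---|
| 20% | 19.5% | 13.0% | 11.7% | 4.6% |
| 30% | 29.3% | 19.3% | 17.4% | 6.9% |
| 40% | 39.1% | 25.6% | 23.0% | 9.0% |

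Half the shifts are upward, and the mean log shift is below 0.0005, so there is no systematic bias in the geometric mean.

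**Effect on F.** F for one SC dose is a ratio of geometric means, so dropping an SC AUC(0-∞) value moves it by the same percentage. Starting from 40%, the earlier-study bioavailability in Protocol 3.2, the median change is 40 × 4.63% = 1.85, 40 × 6.86% = 2.74 and 40 × 9.00% = 3.60 percentage points.

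**The case against.** The preamble opens the whole procedure, and step 2e is one step within it. On that reading the conflict is a matter of drafting. The split at six also has a stated reason: below six the SAP considers a range test unreliable, so it falls back on showing both results. A fixed minimum fall in SD is a property of any such cut-off, and it is the intended effect when the removed value is an assay or sampling error. The harm depends on how often valid values go, and that is unknown, since use is optional and starts from a value already thought atypical. Exclusions are documented, special handling of data is to be recorded in the study report, whole profiles cannot be removed this way, and a 10-value summary can be rebuilt from the listings. The table shells, which are not available here, might show more. PK is secondary and nothing is tested.

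Much of this stands, and it limits the weight of the point. The 21.6% can only be an upper bound, and nothing is hidden. But if the preamble governs, the choice between keeping and dropping a flagged value is left undefined. Documenting or listing an exclusion is also not the same as reporting the summary with the value in. The reason given for the split explains why no test is run below six. It does not explain why the second summary is unnecessary at 6 to 10, where the limit sits at about two whole-cohort SDs or less.

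**Conclusion.** The concern holds. Step 2e and the preamble disagree on whether a flagged value must go, and at the planned cohort size the SAP requires no summary that includes it. For a first deletion at n=10 the log-scale SD falls by at least 25%; this is algebra and depends on no assumption about the data. The floor applies to single cohorts and is smaller for pooled sets (15.4% at n=20, 11.1% at n=30), so it should not be carried over to the pooled bioavailability calculations. The 21.6% assumes clean log-normal data, testing of every cohort and deletion of every flag. The CV, geometric-mean and F illustrations rest on assumed CVs and, for F, on the earlier-study 40%. Because PK is secondary and descriptive and exclusions can be traced, the consequence is minor to moderate. It should still be fixed.

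**What to change.** Make two wording changes in SAP 9.3.1.

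1. In step 2e, replace the mandatory exclusion with a statement that the value is flagged as a potential outlier, so that it agrees with the preamble.
2. For six or more values, require the PK summaries, and F where affected, both with and without any flagged value, as the SAP already does below six. This should apply to Cmax and AUC(0-tlast) as well as to AUC(0-∞) and half-life, and to every value flagged under the repeat clause.

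The cost is the SAP edit plus an extra table row or footnote in the tables where a value is flagged. Design, data collection and subject management do not change.
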